## Appendix A

## Appendix A

|      |   |  |  |
|------|---|--|--|
| 15   | Patients with history of osteonecrosis of the jaw or who are, according to the clinical judgment of the investigator, at high risk to develop osteonecrosis of the jaw, including poor oral hygiene, scheduled invasive dental procedures, high doses of bisphosphonates and/or chemotherapy to treat malignancy. | 
Measured start of all available data and including day of drug initiation in inpatient or outpatient care setting (any diagnosis position):
 
History of osteonecrosis of the jaw:
 
ICD-9 diagnosis: 733.45
ICD-10 diagnosis: M87.180
   |  |
| 16   | Patients with history of atypical subtrochanteric or diaphyseal femoral fractures, according to the diagnostic criteria of the American Society for Bone and Mineral Research Task Force (Shane et al. 2010).   | 
Measured start of all available data and including day of drug initiation in inpatient or outpatient care setting (any diagnosis position):
 
ICD-9 diagnosis: 733.15, 821.0x, 821.1x
ICD-10 diagnosis: M84.75, S72.3x
   |  |
| 17   | Active or recent history of significant upper gastrointestinal disorders, such as esophageal disorders which delay esophageal transit or emptying (e.g. stricture or achalasia).  | 
Measured 365 days prior to and including day of drug initiation in inpatient or outpatient care setting (any diagnosis position):
 
ICD-9 diagnosis: 530.x
ICD-10 diagnosis: K22.x
   |  |
| 18   | Unable to stand or sit in the upright position for at least 30 minutes.   | N/A  |  |
| 19   | Poor medical or psychiatric condition for participating in a clinical study, in the opinion of the investigator.  | 
Measured on the day of drug initiation:
 
CCI >=10 (life expectancy less than the expected duration of the trial)
   |  |
| 20   | History of excessive consumption of alcohol or abuse of drugs in the 1 year prior to Visit 2, in the opinion of the investigator.   | 
Measured 365 days prior to and including day of drug initiation in inpatient or outpatient care setting (any diagnosis position):
 
Alcohol Abuse or Dependence
ICD-9 diagnosis: 291.xx, 303.xx, 305.0x, 571.0x, 571.1x, 571.2x, 571.3x, 357.5x, 425.5x, E860.0x (CMS has not released mapping for new ICD10 for this code), V11.3x
ICD-10 diagnosis: F10.0x, K70.0x, G62.1, I42.6, 099.31x
 
OR
 
Drug Abuse or Dependence
ICD-9 diagnosis: 292.xx, 304.xx, 305.2x-305.9x, 648.3x
ICD-10 diagnosis: F11.x, F12.x, F13.x, F14.x, F15.x, F16.x, F17.2x, F18.x, F19.x, F55.2, G62.0, 099.32x
 
OR
 
Non-compliance
ICD-9 diagnosis: V45.12, V15.81
ICD-10 diagnosis: Z91.19, Z91.15
 | 
Paterno, Elisabetta et al. "Cardiovascular outcomes associated with canagliflozin versus other non-gliflozin antidiabetic drugs: population based cohort study." BMJ 2018;360:k119
http://dx.doi.org/10.1136/bmj.k119
 
Paterno, Elisabetta et al. "Empagliflozin and the Risk of Heart Failure Hospitalization in Routine Clinical Care: A First Analysis from the Empagliflozin Comparative Effectiveness and Safety (EMPRISE) Study." Circulation 2019 Apr 8. doi: 10.1161/CIRCULATIONAHA.118.039177
 |
| 21.1 | Previous treatment with the following bone active drugs is allowed but treatment must be discontinued at Visit 1 or at the time indicated below:
1. Oral bisphosphonates (including alendronate, risedronate, ibandronate, etidronate).  | 
Measured 180 days prior to and 1 day before the day of drug initiation:
 
Generic names:
Alendronate, Ibandronate, Risedronate, Etidronate, Tiludronate
   |  |
| 21.2 | 2. SERMs, calcitonin, estrogen (oral, transdermal, or injectable), progestin, estrogen analog, estrogen agonist, estrogen antagonist or tibolone, androgens, strontium ranelate, or active vitamin D3 analogues.  | 
Measured 30 days prior to and 1 day before the day of drug initiation:
 
Generic names:
SERMs: OSPEMIFENE, RALOXIFENE HCL, ESTROGENS, CONJUGATED/BAZEDOXIFENE ACETATE
Calcitonin
HRT: estrogens, progestins, androgens
  | 
Strontium not approved in USA for treatment of osteoporosis.
 
Vitamin D3 analogues over the counter
   |
| 21.3 | Intravenous zoledronate, if the last dose was administered at least 12 months before Visit 1.   | 
Measured 365 days prior to and 1 day before the day of drug initiation:
 
Generic name:
Zoledronic Acid
   |  |
| 21.4 | Intravenous ibandronate or pamidronate, if the last dose was administered at least 3 months before Visit 1.   | 
Measured 90 days prior to and 1 day before the day of drug initiation:
 
Generic name:
Ibandronate or pamidronate
CPT codes:
C9229, J1740, C9411, J2430
  |  |
| 21.5 | Subcutaneous denosumab, if the last dose was administered at least 6 months before Visit 1.   | 
Measured 180 days prior to and 1 day before the day of drug initiation:
 
Generic name:
Denosumab
   |  |
| 21.6 | Fluoride unless given at therapeutic doses (> 20 mg/day) for more than 3 months in the 2 years prior to Visit 1, or for more than a total of 2 years, or at any dosages within the 6 months prior to Visit 2 (previous or current use of fluoridated water or topical dental fluoride treatment is permitted).    | N/A  | 
Sodium Fluoride is not used to treat the osteoporosis since 2001/2002 when a RCT and sub meta-analysis showed an increased of risk of fractures in the exp arm
  |
| 21.7 | Prior treatment with PTH, teriparatide, or other PTH analogs; or prior participation in any other clinical trial studying PTH, teriparatide, or other PTH analogs.  | 
Measured 730 days (2 years) prior to and 1 day before the day of drug initiation:
 
Generic names:
parathyroid hormone , teriparatide, abaloparatide
Brand names:
Abaloparatide (Reclast®), Teriparatide (Forteo®), Doseyab (Abaloparatide)
  |  |
| 22   | Known hypersensitivity to teriparatide or risedronate, or to any diluents or excipients of teriparatide or risedronate 35 mg/week oral tablet.  | N/A  |  |

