| Excluded based on Exclusion criteria #3.3 - Cushing syndrome and other disorders of adrenal glands                   | -35               | 6383               | -62               | 11167              |
| Excluded based on Exclusion criteria #3.4 - Hyperparathyroidism and hypoparathyroidism                               | -60               | 6323               | -86               | 11081              |
| Excluded based on Exclusion criteria #3.5 - Intestinal malabsorption   | -27               | 6296               | -41               | 11040              |
| Excluded based on Exclusion criteria #4 - Hypercalcemia and Hypocalcemia   | -14               | 6282               | -23               | 11017              |
| Excluded based on Exclusion criteria #5 - Malignant neoplasm, excluding non-melanoma skin cancer                     | -500              | 5782               | -936              | 10081              |
| Excluded based on Exclusion criteria #6 - End-stage liver disease (ESLD)   | -31               | 5751               | -51               | 10030              |
| Excluded based on Exclusion criteria #7 - End-stage renal disease (ESRD)   | -6                | 5745               | -14               | 10016              |
| Excluded based on Exclusion criteria #8 - Nephrolithiasis or urolithiasis  | -52               | 5693               | -109              | 9907               |
| Excluded based on Exclusion criteria #9 - Kyphoplasty or vertebroplasty  | -17               | 5676               | -47               | 9860               |

|   |      |             |       |             |
|---|------|-------------|-------|-------------|
| Excluded based on Exclusion criteria #10 - Osteonecrosis of the jaw                                 | 0    | 5676        | -2    | 9858        |
| Excluded based on Exclusion criteria #11 - Atypical subtrochanteric or diaphyseal femoral fractures | -28  | 5648        | -55   | 9803        |
| Excluded based on Exclusion criteria #12 - Upper gastrointestinal disorders                         | -170 | 5478        | -221  | 9582        |
| Excluded based on Exclusion criteria #13 - CCI (180 days)   | -2   | 5476        | -1    | 9581        |
| Excluded based on Exclusion criteria #14 - Drug addiction or alcohol abuse or not compliant         | -91  | 5385        | -58   | 9523        |

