| Hypoglycemia; n (%)   | 54 (1.4%)            | 17 (2.0%)            | -0.046    | 56 (0.9%)            | 24 (1.5%)            | -0.055    | 110 (1.1%)    | 041 (1.7%)    | -0.051    |
| GI Conditions   |                      |                      |           |                      |                      |           |               |               |           |
| Upper GI (Diseases of esophagus, stomach and duodenum); n (%)   | 852 (22.0%)          | 254 (29.8%)          | -0.179    | 861 (13.3%)          | 334 (21.3%)          | -0.213    | 1,713 (16.6%) | 588 (24.3%)   | -0.192    |
| GI bleeding; n (%)  | 167 (4.3%)           | 30 (3.5%)            | 0.041     | 269 (4.2%)           | 54 (3.5%)            | 0.036     | 436 (4.2%)    | 084 (3.5%)    | 0.036     |

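### Exclusion 20 removes women coded with nicotine dependence under ICD-10 but not under ICD-9, although its concept is alcohol or drug abuse

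*Combined protocol and SAP*

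**What the plan says.** Exclusion 20 in Appendix A states its trial concept as "History of excessive consumption of alcohol or abuse of drugs in the 1 year prior to Visit 2". Tobacco is not named. The claims version looks back 365 days and combines three groups: alcohol, drugs and non-compliance.

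- ICD-9 alcohol codes begin "291.xx, 303.xx, 305.0x, 571.0x, 571.1x, 571.2x, 571.3x".
- ICD-9 drug codes are "292.xx, 304.xx, 305.2x-305.9x, 648.3x".
- ICD-10 drug codes begin "F11.x, F12.x, F13.x, F14.x, F15.x, F16.x, F17.2x, F18.x, F19.x".
- The ICD-10 alcohol entry for F10 is printed as F10.0x.

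Exclusion 17 concerns significant upper gastrointestinal disorders. It uses "ICD-9 diagnosis: 530.x" on the ICD-9 side and K22.x on the ICD-10 side.

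The Section 5.3 flowchart numbers its rows differently: exclusion 20 is row #14 and exclusion 17 is row #12. Section 5.2.1 sets cohort entry from January 2004 to December 2018 (MarketScan) or March 2020 (Optum). The head of Appendix A says that full ICD-10 lists are kept in an external folder and that ICD-9 codes were converted with a mapping macro. In the matched table of Appendix B, smoking carries the asterisk that marks a variable in the propensity score model.

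**The concern.** An exclusion that emulates a trial criterion should select the same kind of patient whichever coding system recorded her. This one does not. Two otherwise identical women, each with a tobacco code in the year before initiation, get opposite eligibility decisions according to which system was in force. Tobacco dependence is also outside the stated criterion.

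The design already has a place for smoking, as a confounder to be balanced. Using it as an exclusion in one era only removes some smokers by rule and leaves the others to the propensity score. What is at stake is who enters the cohort and how closely the cohort follows the trial.

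**Working it through.** **Code comparison for exclusion 20.** Code meanings are from the standard ICD classifications; the document does not spell them out.

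| Concept | ICD-9 printed | ICD-10 printed |
|---|---|---|
| Alcohol dependence or abuse | 303.xx, 305.0x | F10.0x |
| Tobacco or nicotine | none (305.1 lies between 305.0x and 305.2x) | F17.2x |
| Other drugs | 292.xx, 304.xx, 305.2x-305.9x | F11.x-F16.x, F18.x, F19.x |

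The ICD-9 side steps over 305.1. The ICD-10 side names nicotine dependence.

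**Flowchart row #14 (Section 5.3), reproduced first.**
- Optum: 5,476 − 91 = 5,385, as stated. 91/5,476 = 1.7%.
- MarketScan: 9,581 − 58 = 9,523, as stated. 58/9,581 = 0.6%.
- Together: 91 + 58 = 149, and 149/(5,476 + 9,581) = 149/15,057 = 1.0%.

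This row counts alcohol, drugs and non-compliance in all years, so 149 is a ceiling on nicotine exclusions at this step. Against the final cohort of 4,728 + 8,029 = 12,757 it is 149/12,757 = 1.2%. The net number regained would be no higher, since rows #15 to #21 could still remove some of these women.

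**How much of the cohort was coded in the later era.** The document gives no switch date. I assume that the 2016-onward band in Appendix B approximates ICD-10 coding; with a 365-day look-back the match is not exact.
- Optum: (623 + 294)/4,728 = 917/4,728 = 19.4%.
- MarketScan: (539 + 282)/8,029 = 821/8,029 = 10.2%.
- Before matching, by arm: teriparatide 576/2,418 = 23.8%, risedronate 1,162/10,339 = 11.2%.
- After matching: risedronate 435/2,167 = 20.1%, teriparatide 449/2,167 = 20.7%.

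Both coding systems therefore matter, and the later one weighs more on teriparatide initiators before matching but not after.

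**The two further pairs.**
- Alcohol: 303.xx and 305.0x cover dependence and abuse. F10.0x as printed does not reach F10.1x or F10.2x.
- Upper GI: 530.x is the whole esophagus category. K22.x omits K20 (esophagitis) and K21 (reflux).
- Row "Excluded based on Exclusion criteria #12 - Upper gastrointestinal disorders" removed 170/5,648 = 3.0% (Optum) and 221/9,803 = 2.3% (MarketScan), together 391/15,451 = 2.5%.
- The covariate "Upper GI (Diseases of esophagus, stomach and duodenum); n" is still present in (1,713 + 588)/12,757 = 2,301/12,757 = 18.0% of the final cohort.

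**The case against.** **The printed ICD-10 lists are incomplete.** Appendix A says that the full lists are elsewhere, so a code missing from the page may be present in the list that was run. This stands for the alcohol and upper GI pairs, which rest on F10.1x, F10.2x, K20 and K21 not being printed. F10.0x could also be a misprint or misreading, since the obstetric codes in the same cell appear with a zero for a letter. It does not answer the nicotine point: F17.2x is positively printed, and the ICD-9 list is not described as shortened.

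**No effect on the comparison is shown.** A reader might infer biased arms from the unmatched figures: later entry (23.8% versus 11.2%), smoking (9.6% teriparatide versus 6.2% risedronate) and upper GI disease (24.3% versus 16.6%). The rule applies to both arms alike at any date, and all three variables are in the propensity score. After matching, risedronate versus teriparatide, they stand at 20.1% versus 20.7%, 8.4% versus 8.5% and 22.2% versus 22.7%. This objection stands in full.

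**Other inferences that the documents do not support.**
- Taking Optum's higher row #14 rate (1.7% versus 0.6%) as the mark of F17.2x. Smoking is recorded about twice as often in Optum's final cohort (478/4,728 = 10.1% versus 398/8,029 = 5.0%), and the row mixes several reasons. The same reasoning fails for upper GI: a list broader under ICD-9 should remove more in MarketScan, yet it removes less (2.3% versus 3.0%).
- Multiplying smoking prevalence by the 1,738 entrants from 2016 on. Those women were retained, not excluded. Prevalence runs from 4.5% to 14.4% across the database and arm columns, and the product at the top, 0.144 × 1,738 = 250, exceeds the 149 removed for all reasons.
- Concluding from 2.5% removed and 18.0% remaining that 530.x was not run. The covariate also covers stomach and duodenum, so the contrast justifies a check and proves nothing.

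**Conclusion.** The nicotine mismatch holds on the printed definitions. Exclusion 20 removes women for a tobacco code under ICD-10 only, outside the criterion it emulates. It is a defect of eligibility and of fidelity to the trial. Its size is at most 149 women at that step, about 1.0% of those reaching it; the actual number cannot be computed, because nothing is reported by code or coding era. Bias in the matched hazard ratio is not shown.

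The conclusion rests on the standard meaning of 305.1 and F17.2x, and on the printed list being the one applied. If the executed list lacks F17.2x, the printed definition still needs correcting. The alcohol and upper GI mismatches are queries to settle against the executed lists, not established errors.

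**What to change.** Delete F17.2x from exclusion 20 and leave smoking to the propensity score. Re-run the flowchart and the matching before the comparative analysis; the date and results fields in Section 13 are blank, so on this document there is still time.

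In the same pass, compare the executed lists with the printed ones for alcohol (303.xx and 305.0x versus F10.0x) and upper GI (530.x versus K22.x). Align each pair to one stated concept in both coding systems, and print the list that was run. The upper GI rule need not be narrowed to disorders that delay transit, because the trial wording offers those as examples of significant disease.

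The cost is a small code edit, a re-run of the flowchart, matching and balance tables, and a small change in cohort size, with Section 10 power updated to the new matched numbers.

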| Excluded based on Exclusion criteria #15 - Oral bisphosphonate use                                  | -499 | 4886        | -1024 | 8499        |
| Excluded based on Exclusion criteria #16 - SERMs, Calcitonin, HRT                                   | -101 | 4785        | -321  | 8178        |
| Excluded based on Exclusion criteria #17 - Zoledronic acid use                                      | -2   | 4783        | -7    | 8171        |
| Excluded based on Exclusion criteria #18 - Intravenous ibandronate or pamidronate                   | -1   | 4782        | -1    | 8170        |
| Excluded based on Exclusion criteria #19 - Denosumab use  | -10  | 4772        | -4    | 8166        |
| Excluded based on Exclusion criteria #20 - PTH or PTH analogue use                                  | -44  | 4728        | -137  | 8029        |
| Excluded based on Exclusion criteria #21 - Romosozumab  | 0    | 4728        | 0     | 8029        |
| Final cohort  |      | 4728 |       | 8029 |

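### The zoledronic acid, denosumab, romosozumab and PTH-analogue exclusions are defined by drug name alone, so their washouts may miss doses recorded only under procedure codes

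*Combined protocol and SAP*

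**What the plan says.** The prior-treatment exclusions are in Appendix A, with trial wording in one column and the claims implementation in the next. The Section 5.3 flowchart numbers them differently, so both numbers are given here.

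- **21.3 (flowchart #17), zoledronic acid.** Trial rule: "Intravenous zoledronate, if the last dose was administered at least 12 months before Visit 1". Window: "Measured 365 days prior to and 1 day before the day of drug initiation". Identifier: "Generic name : Zoledronic Acid". No procedure code.
- **21.4 (#18), intravenous ibandronate or pamidronate.** Generic names plus four codes: "C9229, J1740, C9411, J2430".
- **21.5 (#19), denosumab.** Trial rule: "Subcutaneous denosumab, if the last dose was administered at least 6 months before Visit 1". Window 180 days. Identifier: "Generic name : Denosumab". No procedure code.
- **21.7 (#20), PTH and analogues.** Window 730 days. Generic and brand names only.
- **26 (#21), romosozumab.** Window 180 days. Generic name only.

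The exposure row of Appendix A defines teriparatide by generic name, NDC, brand name and procedure code J3110. The header of Appendix A refers readers to a shared folder for further or missing detail. It explains that ICD-10 lists are left out because of cell-size limits. Section 13 (Comparative Analyses) has not been filled in.

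**The concern.** The trial wording describes zoledronate as intravenous and denosumab as subcutaneous, with the last dose administered at a stated time. Claims databases may record such doses as a pharmacy dispensing, as a procedure-coded medical claim, or as both. The plan acts on this in 21.4 and in the teriparatide exposure row, but not in the four rows at issue.

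If the name search reaches pharmacy records only, a woman whose infusion or injection was billed solely under a procedure code passes the washout. She would enter the cohort with a recent dose of a bone-active drug that the trial required to be out of the way. The exclusion is also the only protection against this. The Appendix B covariates include SERMs and hormone therapy, but not prior zoledronic acid, denosumab, romosozumab or PTH analogues, so matching does not balance that history directly.

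**Working it through.** **1. Flowchart arithmetic (Section 5.3).** The subtractions agree:

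- Optum: 4,785 − 2 = 4,783; − 1 = 4,782; − 10 = 4,772; − 44 = 4,728; − 0 = 4,728.
- MarketScan: 8,178 − 7 = 8,171; − 1 = 8,170; − 4 = 8,166; − 137 = 8,029; − 0 = 8,029.

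**2. Share removed at each step, both databases pooled.** Share = women removed / women remaining before the step.

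| Step | Procedure codes printed? | Window | Removed / at risk | Share |
|---|---|---|---|---|
| #15 oral bisphosphonates | no | 180 d | (499 + 1,024) / (5,385 + 9,523) = 1,523 / 14,908 | 10.2% |
| #17 zoledronic acid | no | 365 d | (2 + 7) / (4,785 + 8,178) = 9 / 12,963 | 0.07% |
| #18 IV ibandronate/pamidronate | yes | 90 d | (1 + 1) / (4,783 + 8,171) = 2 / 12,954 | 0.02% |
| #19 denosumab | no | 180 d | (10 + 4) / (4,782 + 8,170) = 14 / 12,952 | 0.11% |
| #20 PTH analogues | no | 730 d | (44 + 137) / (4,772 + 8,166) = 181 / 12,938 | 1.4% |
| #21 romosozumab | no | 180 d | 0 / (4,728 + 8,029) = 0 / 12,757 | 0% |

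The zoledronic acid and denosumab shares are what under-capture would produce, but also what rare use would produce. Step #18 does not separate the two. It carries codes and removed still fewer, but its window is only 90 days, and ibandronate had already been searched by name over 180 days at step #15. A zero for romosozumab cannot separate no use from no capture.

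**3. Size in the matched cohort.** The documents do not give the number of users visible only through procedure codes. *Assumption:* 1% to 5% of the 4,334 matched patients are undetected recent users.

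- Patients: 0.01 × 4,334 ≈ 43; 0.05 × 4,334 ≈ 217.
- Expected primary events among them, at the pooled 17.8 per 1,000: 43 × 0.0178 ≈ 0.8; 217 × 0.0178 ≈ 3.9, out of about 77.

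**4. Cost in power.** With events d = N × risk and 1:1 allocation, power = Φ(√(d/4) × |ln HR| − 1.96).

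- The plan's figure (Section 10): d = 4,334 × 0.0178 = 77.1452; √(77.1452/4) × |ln 0.44| = 4.392 × 0.821 = 3.605; Φ(3.605 − 1.960) = 0.950. This reproduces the stated 0.950063363.
- 1% removed: d = 76.37, power 0.948.
- 5% removed: d = 73.29, power 0.940.

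**5. Illustration of possible bias.** *Assumption:* all missed users are in the teriparatide arm (2,167 women), making up 43/2,167 = 2.0% or 217/2,167 = 10.0% of it, and their fracture risk is doubled or halved.

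- Doubled: 0.44 × 1.02 ≈ 0.45; 0.44 × 1.10 ≈ 0.48.
- Halved: 0.44 × 0.99 ≈ 0.44; 0.44 × 0.95 ≈ 0.42.

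Neither the allocation nor the risk multipliers come from the documents.

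**The case against.** **The codes may have been applied without being printed.** The platform's name search may map to procedure codes, and the shared folder may list them. This stands as a possibility, and it is why the fix begins with a statement of what was run. It does not dispose of the point. The omission that the Appendix A header explains is that of ICD-10 lists, while procedure codes are printed in several other rows. A reader of the plan cannot tell whether the stated washouts were delivered.

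**Code printing is uneven throughout.** This is correct. A reader might infer that every other infused or injected drug has a code, but 21.7 has none, and 21.2 names hormone therapy without codes although its trial text covers injectable estrogen. The gap in 21.7 may be narrower than in the other rows, because prior teriparatide use is also screened by the new-user washout in Section 5.2, if the exposure definition with J3110 was used there.

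**The low counts could be genuine.** This also stands. The oral bisphosphonate share concerns a different drug class and a larger denominator, so it is no benchmark for expected use of zoledronic acid or denosumab.

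**Missed users need not cluster in one arm.** A reader might infer from the unmatched tables that teriparatide starters are later-line patients and so hold most of the missed users. Pooled hip or femur fracture history is 8.6% against 4.3%, and other fractures are 13.3% against 6.7%. After matching, these are 6.8% against 6.7% and 11.8% against 12.0%, with mean endocrinologist visits of 1.28 against 1.33 − 0.04 = 1.29. Balance on these markers does not guarantee balance on prior infusions, but the documents do not show a concentration in either arm.

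**Conclusion.** The point holds as a gap in definition. Four washouts are specified by drug name only, while the plan's own practice for comparable drugs is to add procedure codes. As written, they may miss doses recorded only on medical claims, and the propensity score has nothing that directly corrects for this.

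It would go too far to say that recent users do remain in the cohort, or that most doses are missed. The documents contain no count of missed users and do not say that the name search was limited to pharmacy claims. Counts of 9 and 14 do not establish it. The direction of any bias is also unknown, since residual effect and withdrawal would push the hazard ratio opposite ways. The illustration moves it from 0.44 to between about 0.42 and 0.48, but only under assumed allocation and risk.

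This is a cheap improvement worth making before outcomes are compared, and not a demonstrated flaw in the primary estimate.

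**What to change.** State whether procedure codes were applied for 21.3, 21.5, 21.7 and 26. Define each by generic name or NDC, or by the applicable HCPCS/CPT codes in force over the cohort entry period, as in 21.4 and the exposure row, and print the codes in Appendix A. The windows stay as they are.

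If the codes were not already applied, re-run the flowchart and the 1:1 matching before Section 13 is completed, and report revised counts for exclusions #17, #19, #20 and #21.

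Extending the codes to the treatment list in inclusion criterion 3 is optional. That step (flowchart inclusion #4) removed only 3 and 18 women, and its list already includes risedronate through the day of initiation.

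The cost is a code-list edit, one re-run and a slightly smaller matched cohort, with the modest power loss shown in the working.
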